
When biopsies of lesions are scheduled on treatment days (Table 8), they should occur prior to injection of talimogene laherparepvec. When injecting liver lesions, only lesions that have been visualized on CT or MRI multiphase scans used for tumor assessments may be injected. New lesions that have appeared on injection guidance CT scans or US between tumor assessments CT or MRI scans, may not be injected until they have been visualized on tumor assessment CT or MRI scans. All reasonably injectable lesions should be injected with the maximum dosing volume available on an individual dosing occasion (Table 3 and Table 4).

For cutaneous, subcutaneous or superficial nodes, calipers or ruler can be used to measure lesions for injection.

Table 4. PART 2 Only: Talimogene Laherparepvec Injection Volume Guideline Based on Tumor Size for Cutaneous, Subcutaneous and Nodal Lesions

Tumor Size (longer dimension)	Maximum Injection Volume
≥ 10 cm ^a	8.0 mL
≥ 7.5 to < 10 cm ^a	6.0 mL
≥ 5.0 cm to < 7.5 cm ^b	4.0 mL
≥ 2.5 cm to < 5.0 cm	2.0 mL
≥ 1.5 cm to < 2.5 cm	1.0 mL
≥ 0.5 cm to < 1.5 cm	0.5 mL
< 0.5 cm	0.1 mL

^a Volumes > 4.0 mL are only to be used if 8.0 mL is the MTV determined from Part 1 and is allowed in Part 2.

^b If the MTV from Part 1 is determined to be 4 mL, then maximum volume for lesions ≥ 5 cm, including those ≥ 7.5 cm, is 4.0 mL.

On each treatment day, prioritization of injections is recommended as follows:

Part 1:

- **As of Protocol Amendment 6 (dated 26 October 2021), intrahepatic injections of talimogene laherparepvec and liver biopsies are no longer performed in this study.** Any new injectable liver tumor that has appeared on tumor assessment CT or MRI scans since the start of treatment (from newest to oldest). New liver lesions that appear between tumor assessments scans on the CT scans or US used for needle guidance should not be injected until they have been imaged and measured on tumor assessment CT or MRI scans. Lesion selected for injection must not be located, in the Investigator's opinion, where any potential tumor swelling after

injection may lead to significant morbidity or obstruction or where there may be significant risk of bleeding.

- By tumor size, beginning with the largest liver tumor.
- Any previously uninjectable liver tumor(s) that are now large enough to inject.

Part 2:

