*** Bone Lesions:**

- Bone scans, PET scans or plain films are not considered adequate imaging techniques to measure bone lesions. However, these techniques can be used to confirm the presence or absence of bone lesions.
- Osteolytic (lytic) bone lesions or mixed lytic-blastic lesions, with identifiable soft tissue components, that can be evaluated by cross-sectional imaging technique such as CT or MRI can be considered as measurable lesions if the soft tissue component meets the definition of measurability described above. Only the soft tissue component of the bone lesion should be measured.
- Many osteoblastic (blastic) bone abnormalities can be benign and should not be selected as baseline lesions. An isolated new small blastic lesion should not be selected as a new lesion unless there is demonstrated growth on subsequent scans. Multiple new blastic lesions that are clearly cancerous may be considered for new lesions.

Cystic Lesions:

- Lesions that meet the criteria for radiographically defined simple cysts should not be considered as malignant lesions (neither measurable or non-measurable) since they are, by definition, simple cysts.
- Cystic lesions thought to represent cystic metastases can be considered as measurable lesions, if they meet the definition of measurability described above. However, if non-cystic lesions are present in the same subject, these are preferred for selection as target lesions. If a cystic lesion is clearly cancerous and has both cystic and solid components, then the complete lesion should be measured including both components without excluding the cystic portion of a cystic tumor lesion when measuring.

Lesions with Prior Local Treatment:

Tumor lesions situated in a previously irradiated area, or an area subject to other loco-regional therapy, should not be considered measurable unless there has been demonstrated progression in the lesion.

Baseline Documentation of “Target” and “Non-Target” Lesions:

Baseline evaluations will be used to prospectively identify all sites of disease present as close as possible to the enrollment and never more than 4 weeks before the enrollment date. Sites of disease will be characterized as either target or non-target lesions.

Baseline Documentation of Target Lesions:

Up to 10 target lesions (a maximum of 5 per organ) will be chosen to measure over the course of therapy. Pathological lymph nodes that are defined as measurable must meet

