the criterion of a short axis of ≥ 15 mm by CT scan in order to be identified as target lesions.

The distribution of these target lesions should be representative of the subject's overall disease status. Target lesions should be selected on the basis of their size (lesions with longest diameter) and suitability for accurate repeated measurements by imaging techniques. In situations where larger lesions cannot be accurately measured repeatedly (eg, near the diaphragm where respiratory changes may affect measurements), smaller lesions that meet criteria for measurability may be selected instead.

A sum of the diameters (longest for non-nodal lesions, short axis for nodal lesions) for all target lesions will be calculated and reported as the baseline sum diameters. The baseline sum of diameters will be used as reference by which to characterize the objective tumor response.

Baseline Documentation of Non-Target Lesions:

All other lesions (or sites of disease), including any measurable lesions that were not chosen as target lesions and pathological lymph node with short axis ≥ 10 mm but < 15 mm, should be identified as non-target lesions. Measurable non-target lesions (ie, lesions in an organ beyond the allowed maximum number of targets that would otherwise qualify as target lesions) should also be recorded and assessed qualitatively over the course of therapy. Non-measurable non-target disease measurements are not required, but these lesions are evaluated at each timepoint and will be evaluated as 'present', 'absent', or in rare cases 'unequivocal progression'. If a significant partial response (PR) is observed in a non-target lesion, it should be described as a comment.

Follow-up Assessment of Tumor Lesions:

At each subsequent tumor assessment, the sum of diameters of target lesions identified at baseline plus the sum of diameters of up to 10 (maximum 5 per organ) new measurable lesions (ie, accurately and serially measured in at least 2 dimensions and for which the longest diameter is ≥ 10 mm for non-nodal lesions or the short axis is ≥ 15 mm for non-nodal lesions) are added together to provide the total tumor burden. If more than 10 new measurable lesions total (or 5 per organ) are present at a single timepoint, the new measurable lesions should be selected on the basis of their size and suitability for accurate repeated measurements by imaging techniques (CT or MRI). If

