#### **Lesion objective response rate (L-ORR)**

Lesion objective response rate (L-ORR) is a response rate at the lesion level in injected vs uninjected lesions and is defined as the incidence among a set of lesions analyzed of L-CR or L-PR.

Response at the lesion-level will be censored at the earliest **after the start of the first subsequent anticancer therapy**, or on or after the event of merging with another lesion, or complete or partial removal/reduction of any target lesion which contained cancer on pathology evaluation or pathology results were unknown. If a lesion splits, the sum of the length of the split lesions will be added together prior to analysis.

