## **9.5 Efficacy Analyses**

The efficacy analysis will be conducted separately for Part 1 and Part 2, using the Full Analysis Set. The efficacy analysis in Part 1 will be conducted overall and by group/cohort. The efficacy analysis in Part 2 will be performed overall and by group/tumor type, unless otherwise specified.

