
and uninjected lesions, DCR, PFS, and OS by primary tumor type.
	
primary tumor type. The ORR/DRR/DCR will be estimated with the associated 95% CI. Tumor response endpoints may also be evaluated based on modified RECIST v 1.1 for historical comparison for each tumor type that continues to Stage 2 of Part 2.
 
 
• Kaplan-Meier (K-M) estimates of landmarks (e.g., 1-, 2-, and 3-year rates) and quartiles for DOR/PFS/OS will be provided (Kaplan and Meier, 1958). Greenwood's formula (Kalbfleisch and Prentice, 1980) for standard error will be used to calculate CIs for landmark K-M rates. CIs for K-M quartiles will be estimated (Brookmeyer and Crowley, 1982).
 
• Waterfall plots for maximum tumor burden decrease in the lesion diameter at subject-level and lesion-level will also be provided.
 
• Analysis for response rate in injected vs. uninjected lesions may show the evidence of systemic effect separately in Part 2. Analysis of response at lesion-level will be conducted by lesion type (injected vs. uninjected and liver vs. non-liver), and overall, if appropriate. Wilson's score method with continuity correction (Newcombe, 1998) will be used to calculate an approximate exact CI for between-group differences in binary rates if appropriate.
 
	

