### Appendix C. Wilson's Score Method with Continuity Correction in Calculating the 95% Confidence Intervals for Difference in 2 Independent Proportions

The following formula of interval estimation is extracted from Newcombe 1998 paper:

Assuming

$$X_i \stackrel{i.i.d.}{\sim} \text{Bernoulli}(\pi_1), \text{ where } i = 1, 2, \dots, m.$$

$$Y_j \stackrel{i.i.d.}{\sim} \text{Bernoulli}(\pi_2), \text{ where } j = 1, 2, \dots, n.$$

$$\theta = \pi_1 - \pi_2$$

$$\hat{\pi}_1 = \sum_{i=1}^m x_i / m = a / m .$$

$$\hat{\pi}_2 = \sum_{j=1}^n y_j / n = b / n .$$

Then the  $100(1 - \alpha)\%$  confidence interval for  $\hat{\theta} = \hat{\pi}_1 - \hat{\pi}_2 = a / m - b / n$ , with continuity correction is

$$\delta = \sqrt{\{(a / m - l_1)^2 + (u_2 - b / n)^2\}}$$

$$\varepsilon = \sqrt{\{(u_1 - a / m)^2 + (b / n - l_2)^2\}}$$

$l_1$  and  $u_1$  delimit the interval  $\{\pi_1 : |\pi_1 - a / m| - 1 / (2m) \leq z_{1-\alpha/2} \sqrt{\pi_1(1-\pi_1) / m}\}$  and

$l_2$  and  $u_2$  delimit the interval  $\{\pi_2 : |\pi_2 - b / n| - 1 / (2n) \leq z_{1-\alpha/2} \sqrt{\pi_2(1-\pi_2) / n}\}$ .

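### The planned interval for differences in lesion response treats lesions as independent, although they cluster within subjects, so its true coverage can fall below or rise above 95%

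*SAP*

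**What the plan says.** The Part 2 lesion bullet of SAP Table 9-2 first sets the unit and the comparison: "Analysis of response at lesion-level will be conducted by lesion type (injected vs. uninjected and liver vs. non-liver), and overall, if appropriate". Its next sentence gives the interval: Wilson's "score method with continuity correction (Newcombe, 1998) will be used to calculate an approximate exact CI for between-group differences in binary rates if appropriate". The title of SAP Appendix C describes the method as a 95% interval for a "Difference in 2 Independent Proportions", and its formula starts from two sets of independent, identically distributed Bernoulli observations.

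The lesion response rate in SAP Section 5 "is defined as the incidence among a set of lesions analyzed of L-CR or L-PR", so its denominator is lesions. SAP 6.11 draws those lesions from all Full Analysis Set subjects. Protocol Appendix D sets the maximum number per subject: "Up to 10 target lesions (a maximum of 5 per organ) will be chosen to measure", "plus the sum of diameters of up to 10 (maximum 5 per organ) new" measurable lesions.

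The SAP describes no adjustment for several lesions from one subject, and the sensitivity column of Table 9-2 reads N/A. The condition at the end of the interval sentence states neither when the method would be unsuitable nor what would replace it.

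**The concern.** Lesions in one subject share the host, the tumour biology and the same systemic pembrolizumab, so their responses are likely to be correlated. One subject can also contribute to both sides of the comparison. Independence then fails within each sample and between the two samples, and the two failures act in opposite directions. Clustering within a lesion type makes the stated interval too narrow. A response tendency shared by both types partly cancels in the difference and makes it too wide.

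Which effect dominates depends on how injected lesions are spread over subjects, and the plan does not fix that. Protocol 6.2.1.1 says "All reasonably injectable lesions should be injected with the maximum dosing volume available on an individual dosing occasion", within a daily volume limit. Under Protocol Table 4 a single lesion of 10 cm or more may take all 8 mL, while lesions of 2.5 to under 5 cm take 2 mL each. The injected share can therefore differ widely between subjects.

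The SAP offers the injected-versus-uninjected analysis as possible evidence of an effect beyond the injected site. An interval printed beside that comparison will be read as a 95% interval.

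**Working it through.** **Plan's own figure.** The documents state no coverage, power or sample size for the lesion comparison, so there is nothing to reproduce.

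**Inputs from the documents.** SAP 3.2 expects 10 to 21 subjects per tumour type. Protocol 3.3 gives 53 Part 2 subjects; over six arms that is 53/6 = 8.8. I used 9, 10 and 21.

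**Assumed inputs.** Lesion response of 25% in both groups; 6 or 10 lesions per subject when both types share a subject (3 or 5 per type when balanced); ICC from 0 to 0.6.

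**Step 1: why the error has two directions.** Let subject *i* have m1i and m0i lesions of the two types, with totals M1 and M0, common response rate p and ICC ρ. If both types share the subject's response tendency, then

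Var(difference) = p(1−p) [ (1−ρ)(1/M1 + 1/M0) + ρ Σ(m1i/M1 − m0i/M0)² ].

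Independence gives p(1−p)(1/M1 + 1/M0). The ratio of true to assumed variance is

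R = (1−ρ) + ρ Σ(m1i/M1 − m0i/M0)² / (1/M1 + 1/M0).

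- Types balanced within subjects: the sum is zero and R = 1−ρ. At ρ = 0.4, R = 0.6, and coverage is roughly 2Φ(1.96/√0.6) − 1 = 2Φ(2.53) − 1 = 98.9%.
- Types in different subjects, m lesions each: R = 1 + (m−1)ρ. At m = 5 and ρ = 0.3, R = 2.2, and coverage is roughly 2Φ(1.96/√2.2) − 1 = 2Φ(1.32) − 1 = 81%.

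These are large-sample values without the continuity correction, which raises coverage somewhat.

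**Step 2: simulated coverage of the Appendix C interval** (beta-binomial lesions, 20,000 or more runs per setting). SAP 6.1 requires at least one talimogene laherparepvec dose, so the first four injected-versus-uninjected rows give every subject at least one injected lesion.

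| Setting | ICC | Coverage |
|---|---|---|
| Injected vs uninjected, share varies strongly (Beta(0.5, 0.5)) | 0.2–0.6 | about 76%–95% |
| Injected vs uninjected, share uniform on 0–1 | 0.2–0.6 | about 82%–96% |
| Types balanced within subjects | 0.2–0.6 | about 98%–99.9% |
| The three settings above | 0.1 | about 93%–98% |
| Types in different subjects | 0.2–0.6 | about 73%–96% |
| Independent lesions | 0 | about 96%–98% |

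The lower ends of the first two rows move by a point or two with the way the one-injected-lesion condition is imposed.

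**Step 3: a subject-clustered interval in similar settings.** With n contributing subjects and y1i, y0i responding lesions, take z_i = (y1i − p̂1·m1i)/M1 − (y0i − p̂0·m0i)/M0, variance n/(n−1) · Σz_i², and a t quantile on n−1 degrees of freedom. Coverage was 94% to 99% in runs with a responding lesion in both groups. At 21 subjects, 5 lesions per type, rates of 40% and 20% and ICC 0.1 to 0.5, it was 94.0% to 95.2%, against 76.2% to 97.9% for the planned interval.

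**The case against.** **The plan is conditional and does not name its groups.** This is true. The lesion reading rests on the sentence's place in the lesion bullet. Elsewhere group means non-HCC or HCC: "The efficacy analysis in Part 2 will be performed overall and by group/tumor type, unless otherwise specified". Under that reading the two samples are different subjects, but lesions still cluster within each. With an assumed 43 versus 10 subjects, coverage was 74% to 93%. The condition softens the commitment but leaves the choice until the data are seen.

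**The lowest coverage does not suit the main comparison.** This stands. A reader might infer that coverage near 73% to 75% is to be expected for injected versus uninjected lesions. It needs the two types in different subjects and a high ICC. Because every Full Analysis Set subject received talimogene laherparepvec, that split is not natural here, although an injected lesion need not be one of the measured lesions. It is possible for liver versus non-liver.

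**The direction is not fixed.** A reader might also infer that the interval is always too narrow. It is not: with 1 to 6 or 1 to 10 lesions per subject, one injected and the rest split evenly, coverage was 97% to 99%. Part of any excess comes from the continuity correction, as the independent-lesion row shows. The clustered interval itself reaches 99% in some settings.

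**The analysis is descriptive.** Also true: no decision rule depends on it, and the primary test counts subjects, not lesions. This limits the weight of the point but does not make the stated confidence level right.

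**Conclusion.** The interval is wrong as written for lesion-level differences; the importance is minor to moderate. The mismatch between Appendix C's independence assumption and pooled lesions can be seen in the documents without any simulation. Its size cannot, because they give only maximum lesion counts and neither a correlation nor an injected share. Under the stated assumptions the error matters at ICC 0.2 or more and can go either way; at 0.1 it is small. The documents do not support a claim that the interval is generally too narrow, that coverage in the low 70s is typical, or that any primary conclusion is at risk.

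**What to change.** In the Part 2 lesion bullet of SAP Table 9-2, for lesion-level rates:

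- Replace the Newcombe interval with a subject-clustered interval for the difference. Examples are the linearised variance in Step 3, or GEE with subject as cluster, with a t quantile on contributing subjects minus 1.
- Show the numbers of subjects and lesions in each group.
- Give counts without an interval when a group has no responding lesion or when very few subjects contribute, and state that minimum in advance. At 4 subjects the clustered width ran from 0.37 to 2.60, where 2.0 is the largest possible.
- Limit Appendix C to comparisons of different subjects, such as clearance by HSV-1 serostatus in SAP 9.6.2, where it is suitable.

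I would not add a landmark analysis that fixes injection status early, for example at week 7. It would count lesions injected later as uninjected, in a comparison meant to look for systemic effect.

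**Cost.** A little programming and no new data. At 21 subjects, 5 lesions per type, ICC 0.3 and rates of 40% and 20%, mean width goes from 0.355 to 0.523 with types in different subjects, and from 0.250 to 0.227 with types balanced within subjects. Small arms will have wide intervals: median clustered widths at 9 to 10 subjects ranged from 0.23 to 1.13. At 9 subjects with types in different subjects, up to 24% of runs had no responding lesion in one group, so only counts would be reported.

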**9.5.1 Analyses of Primary Efficacy Endpoint(s)**

**Part 2:**

- ORR per modified irRC-RECIST with intrahepatic injection of talimogene laherparepvec into liver tumors in combination with systemic IV administration

of pembrolizumab separately by tumor type (hormone receptor positive BC, TNBC, CRC, CSCC, BCC, without viral hepatitis)

**9.5.2 Analyses of Secondary Efficacy Endpoint(s)**

[figure not shown]
**Part 1:**

- ORR, BOR, DRR, DOR, response in injected and uninjected lesions, DCR, PFS, and OS separately for non-HCC and HCC tumors in monotherapy and combination cohorts

**Part 2:**

- BOR, DRR, DOR, response in injected and uninjected lesions, DCR, PFS, and OS by primary tumor type arm

**9.5.3 Analyses of Exploratory Efficacy Endpoint(s)**

**9.6 Safety Analyses**

**9.6.1 Analyses of Primary Safety Endpoint(s)**

**Part 1 and Part 2:**

**Table 9-4. Safety Endpoint Summary Table**

Endpoint	Primary Summary and Analysis Method (Specify Analysis Set if FAS is Not Used)	Sensitivity Analysis
Part 1: Monotherapy cohorts 1-4: Subject incidence of DLTs with intrahepatic injection of talimogene laherparepvec into liver tumors in subjects with non-HCC with liver metastases and subjects with HCC without active viral hepatitis. Combination cohorts 5 and 6: Subject incidence of DLTs with intrahepatic injection into liver tumors of talimogene laherparepvec in combination with systemic IV administration of pembrolizumab in subjects with non-HCC with liver metastases and subjects with HCC with and without viral hepatitis.	The subject incidence of DLT will be summarized as a binary variable using the DLT analysis set.	N/A

Part 2: Subject incidence, for each tumor type arm, of treatment-emergent and treatment-related adverse events, including DLTs.	The subject incidence of DLT will be summarized as a binary variable using the DLT analysis set.	N/A
--	--	-----

### 9.6.2 Adverse Events and Disease-related Events

The Medical Dictionary for Regulatory Activities (MedDRA) version **24.1** or later will be used to code all events categorized as adverse events, disease-related events to a system organ class and a preferred term. The CTCAE version 4.03 will be used to grade severity of AEs. All the safety analysis of adverse events will be evaluated in each monotherapy and combination cohorts in Part 1 (by cohort/group) and each tumor type separately in Part 2 (by tumor type arm/group).

The subject incidence of adverse events will be summarized for all treatment-emergent, treatment-related adverse events within the following categories: grade 3, grade 4, grades 3 or 4, serious adverse events, adverse events leading to withdrawal of investigational product, and fatal adverse events.

Additional subject incidence tables will be presented to describe the treatment-emergent and treatment-related adverse events (including all adverse events, grade  $\geq 3$  adverse events, serious adverse events, fatal adverse events, adverse events of interest, adverse events requiring permanent discontinuation of study therapy, and local effects on the tumor[i.e., pain, inflammation and ulceration]). Summaries of treatment-emergent and serious AEs by preferred term will be provided in descending order of frequency. The subject incidence summaries will be provided in 2 ways: within system organ class (SOC) subset by preferred term, and by decreasing order of preferred term frequency. In addition, adverse events and treatment-related adverse events will be tabulated by worst grade within SOC subset by preferred term.

A summary of deaths after initiation of the study through 90 days since the last dose of talimogene laherparepvec or pembrolizumab, whichever is discontinued last will be provided.

Listings will be provided for treatment-emergent and treatment-emergent, treatment-related adverse events (including all adverse events, serious adverse events, fatal adverse events, and adverse events requiring permanent discontinuation of protocol

drug). In addition, screening SAEs prior to study Day 1 and all AEs > 30 (+/-7) days from last dose of study drug will be listed.

